7.1.7 Severity of Adverse Events

The investigator will grade all adverse events for severity. Adverse events listed in the grading scale in Appendix I will be graded according to the criteria in the table. Adverse events not listed in the grading scale will be graded as follows:

- Mild (Grade 1): No interference with activity
- Moderate (Grade 2): Some interference with activity
- Severe (Grade 3): Significant; prevents daily activity
- **Potentially Life-Threatening (Grade 4):** As determined by emergency room visit or hospitalization.

For the study grading scale see Appendix I.

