8.7.2.1 Solicited Adverse Events

With the exception of redness and swelling, all solicited AEs will be summarized according to severity grading scales defined in Section 7.1.7 from "mild" to "potentially life-threatening."

Solicited AEs will be recorded daily until 7 days post-injection (Day 8) using an e-diary. The analyses of solicited AEs will be performed by maximum severity and by treatment group. In addition, solicited AEs ongoing after seven days post-injection (Day 8) will also be recorded as unsolicited AEs.

Frequencies and percentages of participants experiencing each solicited AE will be presented by maximum severity. Summary tables showing the occurrence of any local or any systemic solicited AE overall and at each time point will also be presented.

The severity of redness and swelling, recorded as diameters (mm), will be summarized according to categories based on the largest diameter linear measurement when the local reaction is present:

- Grade 0/absent = 0-24 mm
- Grade 1/mild = 25-50 mm
- Grade 2/moderate = 51-100 mm
- Grade 3/severe = >100 mm
- Grade 4/potentially life threatening = necrosis or exfoliative dermatitis

Refer to Appendix I.

Events reported as not present (0 mm is entered) will be reported as Grade 0.

The following summaries of solicited events will be performed:

- 1. Solicited events by day post-injection for each event and for any event.
- 2. Time of first onset of solicited AEs, for each event and any event.

- 3. Solicited AEs by maximum event severity, for each event and for any event.
- 4. Duration of solicited AEs, for each event and any event.

Solicited AEs, occurrence of at least one event by category (local, systemic), will also be included.

Only participants with at least one observation (i.e., any nonmissing values but excluding "Not done/unknown") for the solicited AEs will be summarized.

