APPENDIX I TOXICITY GRADING SCALE TABLES

*In addition to grading the measured local reaction at the greatest single diameter, the measurement should be recorded as a continuous variable.

**Induration/Swelling should be evaluated and graded using the functional scale as well as the actual measurement.

***Revised by the sponsor

Vital Signs*	Mild (Grade 1)	Moderate (Grade 2)	Severe (Grade 3)	Potentially Life Threatening (Grade 4)
Fever (°C)** (°F)**	38.0 - 38.4 100.4 - 101.1	38.5 - 38.9 101.2 - 102.0	39.0 - 40 102.1 - 104	>40 >104
Tachycardia – beats per minute	101 – 115	116 - 130	>130	ER visit or hospitalization for arrhythmia
Bradycardia – beats per minute***	50 - 54	45 – 49	<45	ER visit or hospitalization for arrhythmia
Hypertension (systolic) – mmHg	141 – 150	151 – 155	>155	ER visit or hospitalization for malignant hypertension
Hypertension (diastolic) – mmHg	91 – 95	96 – 100	>100	ER visit or hospitalization for malignant hypertension

Vital Signs*	Mild (Grade 1)	Moderate (Grade 2)	Severe (Grade 3)	Potentially Life Threatening (Grade 4)
Hypotension (systolic) – mmHg	85 – 89	80 - 84	<80	ER visit or hospitalization for hypotensive shock
Respiratory Rate – breaths per minute	17 – 20	21 - 25	>25	Intubation

EBSI-CV-317-004, Version 5.0 20 Mar 2023

*Participant should be at rest for all vital sign measurements.

**Oral temperature; no recent hot or cold beverages or smoking.

***When resting heart rate is between 60 - 100 beats per minute. Use clinical judgement when characterizing bradycardia among some healthy participant populations, for example, conditioned athletes.

Systemic (General)	Mild (Grade 1)	Moderate (Grade 2)	Severe (Grade 3)	Potentially Life Threatening (Grade 4)
Nausea/vomiting	No interference with activity or 1 – 2 episodes/24 hours	Some interference with activity or >2 episodes/24 hours	Prevents daily activity, requires outpatient IV hydration	ER visit or hospitalization for hypotensive shock
Diarrhea	2 – 3 loose stools or <400 g/24 hours	4 – 5 stools or 400 – 800 g/24 hours	6 or more watery stools or >800 g/24 hours or requires outpatient IV hydration	ER visit or hospitalization
Headache	No interference with activity	Repeated use of non-narcotic pain reliever >24 hours or some interference with activity	Significant; any use of narcotic pain reliever or prevents daily activity	ER visit or hospitalization

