5.9 Adverse Event Toxicity/Severity Grading

With the exception of redness and swelling, all solicited AEs are graded by the investigator according to severity grading scales from "mild" to "potentially life-threatening." The severity of redness and swelling, recorded as a diameter (mm) in the solicited adverse event diary, are summarized according to categories based on the largest-diameter linear measurement when a local reaction is present:

- Grade 0/absent = 0-24 mm.
- Grade 1/mild = 25-50 mm.
- Grade 2/moderate = 51-100 mm.
- Grade 3/severe = >100 mm.
- Grade 4/potentially life threatening = necrosis or exfoliative dermatitis.

Events reported as not present (0 mm is entered) are reported as Grade 0. Similarly, body temperatures recorded by the participant that are below 100.4° result in fever reported as Grade 0/absent.

Solicited AEs other than redness and swelling and unsolicited AEs are graded by the investigator for severity. The severity grading scales (Grade 1 = mild, Grade 2 = moderate, Grade 3 = severe, Grade 4 = potentially life-threatening) that are used for safety assessment in this study are provided in Appendix I of this document and Section 7.1.7 of the Protocol, based on the *FDA Guidance for Industry: Toxicity Grading Scale for Healthy Adult and Adolescent Volunteers Enrolled in Preventative Vaccine Clinical Trials* (2). Note that AEs that result in death are classified as Grade 4 and indicated as resulting in death.

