9.2 Adverse Events

The safety of PXVX0317 in healthy adult and adolescent participants 12 to <65 years of age is evaluated using solicited AEs occurring from IP administration on Day 1 through Day 8, unsolicited AEs through Day 29, and AESI and SAEs and MAAEs though Day 183 EOS. AEs are coded to SOC and PT according to the MedDRA dictionary per Section 5.8. They are coded for severity according to Section 5.9 and Appendix II. Only treatment-emergent AEs are summarized (i.e., excluding those after a participant has given informed consent, but before vaccination). See Section 6.3 for definitions.

Solicited AEs, unsolicited AEs, AESI and SAEs and MAAEs are summarized separately by treatment group and maximum severity for the safety population for all age strata combined. Separate participant data listings of solicited and unsolicited AEs sorted by participant identifier and AE start date are generated.

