APPENDIX II TOXICITY GRADING SCALE

EVENT	MILD (Grade 1)	MODERATE (Grade 2)	SEVERE (Grade 3)	POTENTIALLY LIFE THREATENING (Grade 4)
Fever	≥100.4-101.1°F (≥38.0-38.4°C)	≥101.2-102°F (≥38.5-<39°C)	≥102.1°F-104°F (≥39°C-40°C)	>104°F (>40°C)
Headache	No interference with activity	Some interference with activity, may require repeated use of non-narcotic pain reliever for more than 24 hours	Significant, prevents daily activity, any use of narcotic pain reliever	ER visit or hospitalization
Fatigue	No interference with activity	Some interference with activity	Significant, prevents daily activity	ER visit or hospitalization
Myalgia	No interference with activity	Some interference with activity	Significant, prevents daily activity	ER visit or hospitalization
Nausea	No interference with activity	Some interference with activity	Significant, prevents daily activity	ER visit or hospitalization for hypotensive shock
Vomiting	1–2 episodes/24 hours	>2 episodes/24 hours	Requires IV hydration	ER visit or hospitalization for hypotensive shock
Diarrhea	2-3 loose stools or <400 g/24 hours	4-5 stools or 400- 800 g/24 hours	6 or more watery stools or >800 g/24 hours or requires outpatient IV hydration	ER visit or hospitalization
Injection site pain	Does not interfere with activity	Repeated use of non-narcotic pain reliever > 24 hours or interferes with activity	Use of any narcotic pain reliever or prevents daily activity	ER visit or hospitalization
Injection site erythema/redness	25-50 mm	51 mm-100 mm	>100 mm	Necrosis or exfoliative dermatitis
Injection site induration/swelling	25-50 mm and does not interfere with activity	51 mm-100 mm or interferes with activity	>100 mm or prevents daily activity	Necrosis

Document Approvals Approved Date: 27 Mar 2023

Document Approval Task Verdict: Approve	Director, Biostatistics
Document Approval Task Verdict: Approve	Sr Director, Biostatistics & Data Sciences
Document Approval Task Verdict: Approve	Sr. Manager, Clinical Trials
Document Approval Task Verdict: Approve	VP, Clinical Development

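### The summary tables grade injection-site swelling by diameter alone, while the trial's own scale also counts effect on activity; if that effect was captured, swelling at Grade 2 or higher and at Grade 3 can be understated.

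*Protocol*

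**What the plan says.** **Rule for the tables.** Protocol 8.7.2.1 excepts redness and swelling from the general severity scale and then states: "The severity of redness and swelling, recorded as diameters (mm), will be summarized according to categories based on the largest diameter linear measurement". The bands are 0–24 mm (Grade 0), 25–50 mm (Grade 1), 51–100 mm (Grade 2) and over 100 mm (Grade 3). SAP 5.9 has the same exception and the same bands. The Protocol section closes its list with "Refer to Appendix I".

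**Rule on the scale.** Protocol 7.1.7 says: "Adverse events listed in the grading scale in Appendix I will be graded according to the criteria in the table". Swelling is listed in that table, and a footnote to it adds: "Induration/Swelling should be evaluated and graded using the functional scale as well as the actual measurement". SAP Appendix II carries the same content. Grade 1 is "25-50 mm and does not interfere with activity" and Grade 2 is "51 mm-100 mm or interferes with activity". Grade 3 is met by a diameter over 100 mm or by swelling that stops daily activity. SAP 9.2 says of adverse events in general: "They are coded for severity according to Section 5.9 and Appendix II".

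**Who grades.** Protocol 3.3.10 has the investigator assess the severity of every solicited event under Section 7.1.7 and enter the result on the solicited AE eCRF. SAP 9.2.2 likewise has the investigator assess solicited severity, just as for unsolicited events, and makes no exception. SAP 5.9 does make one: "Solicited AEs other than redness and swelling and unsolicited AEs are graded by the investigator for severity".

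**The concern.** Swelling is graded one way for the tables and another way on the scale, and the two can give different grades for the same reaction. Solicited AEs through Day 8 are a primary safety endpoint (Protocol 8.3.1). The swelling grade feeds Table 14.3.2.2.1 (highest severity, pooled and by age group), Table 14.3.2.3 (Grade 3 or higher) and the Grade 3 or higher lines of the overall summary in SAP 9.2.1. A reader of those tables would reasonably assume that Grade 3 means Grade 3 on the protocol's toxicity scale. For swelling it would mean only a diameter over 100 mm, or necrosis or exfoliative dermatitis at Grade 4.

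The disagreement over who grades adds a practical problem. From the text alone, a programmer cannot tell whether an investigator's swelling grade exists on the eCRF or whether the only source is the diary measurement in millimetres.

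**Working it through.** The plan gives no figure to reproduce here. The check applies both rules to every combination of diameter band and effect on activity. Grade 4 is set aside: Protocol 8.7.2.1 and SAP 5.9 list necrosis or exfoliative dermatitis for both reactions, while the appendices list only necrosis for swelling.

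**Inputs.** Diameter bands come from Protocol 8.7.2.1 and SAP 5.9. Functional criteria come from Protocol Appendix I and SAP Appendix II.

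**Formulas.**
- Table grade T = d, where d = 0 (0–24 mm), 1 (25–50), 2 (51–100), 3 (>100).
- Scale grade S = max(d, f), where f = 0 (no effect on activity), 2 (interferes), 3 (prevents daily activity).

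Because S is a maximum that includes d, S is never below T.

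| Diameter | T | S, no effect | S, interferes | S, prevents |
|---|---|---|---|---|
| 0–24 mm | 0 | 0 | 2 | 3 |
| 25–50 mm | 1 | 1 | 2 | 3 |
| 51–100 mm | 2 | 2 | 2 | 3 |
| >100 mm | 3 | 3 | 3 | 3 |

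The documents do not say whether function counts when the swelling is below 25 mm, so two assumptions are shown.

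- **A, function counts at any size:** 4 × 3 = 12 combinations. T is lower than S in 5 and higher in 0. In 3 of these a Grade 3 is missed, in 4 a Grade 2 or higher is missed, and in 2 the swelling is counted as absent.
- **B, a 25 mm floor applies:** 3 × 3 = 9 combinations. T is lower in 3 and higher in 0. In 2 a Grade 3 is missed, in 2 a Grade 2 or higher is missed, and none is counted as absent.

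These are logical combinations, not frequencies. They establish direction only.

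**Effect of one affected participant**, using planned numbers:
- pooled vaccine: 1/2700 = 0.037%, about 0.04 percentage points
- pooled placebo: 1/450 = 0.22 points
- vaccine in a 12 to <18 or 46 to <65 stratum at its planned minimum: 1/210 = 0.48 points
- placebo in the same stratum: 1/35 = 2.9 points

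Actual denominators will be participants with diary observations (SAP 6.3), so these figures are approximate.

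**Redness.** Both rules grade redness by diameter alone in Grades 1 to 3, so there is no conflict.

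**The case against.** The strongest reply is that the plan does settle which rule the tables use. Protocol 8.7.2.1 opens by taking redness and swelling out of the Section 7.1.7 scale for summaries, and that section is the route to Appendix I. SAP 5.9 does the same. The pointer to Appendix I can be read as the source of the millimetre cut-offs. SAP 9.2 can be read as complementary: Section 5.9 for redness and swelling, Appendix II for the rest. This stands. A reader might infer that the plan leaves the table rule open, but the exception makes diameter-only the rule for summaries. What remains is that this rule contradicts the scale that the same documents set for grading swelling.

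The second reply is that any understatement needs functional data, and these may not exist. The documents describe a ruler and daily measurements in millimetres, and no diary item on how swelling affects activity. The eCRF and table shells are not available, and SAP 1 says that some derivation detail sits in the shells. This also stands, and it makes the understatement conditional. It does not remove the point, because Protocol 3.3.10 and SAP 9.2.2 call for an investigator's grade on every solicited event.

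Third, the consequences are limited. Safety endpoints are reported for information only (Protocol 8.6.2.5.2), both arms share the rule, and pain is graded separately by function. Solicited AEs are listed by participant, and those that are serious, medically attended or ongoing after Day 8 are also recorded as unsolicited (SAP 9.2.2). All of this is correct and is why the point is minor.

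**Conclusion.** The contradiction is real, and its direction within Grades 0 to 3 is certain: the table grade for swelling equals the scale grade or falls below it. Whether any count changes depends on two things that the documents do not show: that functional severity of swelling was recorded, and that some participants had swelling whose effect on activity outranked its size. The number affected cannot be computed and may be zero.

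Two stronger readings should be resisted. The 5 of 12 or 3 of 9 combinations are not a rate of misgrading. Nor do the documents show that severe swelling is in fact undercounted; they show only that the stated rule permits it. No view is taken on which grading rule is right. Severity: minor.

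**What to change.** Reconcile Protocol 3.3.10, 7.1.7, 8.7.2.1 and Appendix I with SAP 5.9, 9.2, 9.2.2 and Appendix II in a short SAP clarification. First confirm whether the investigator's swelling severity is on the solicited AE eCRF.

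- **If it is:** keep the diameter table that Protocol 8.7.2.1 requires. Add swelling by the appendix grade (size and function) to Tables 14.3.2.2.1 and 14.3.2.3, and state whether function counts below 25 mm.
- **If function was not captured:** label the swelling rows as diameter-only, with a footnote that the functional criterion in the appendices was not applied.

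A reader might infer that the SAP alone could make the appendix grade the main table. It could not: Protocol 8.7.2.1 commits to the diameter summary and would have to be aligned first.

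The first route costs one derivation and some table rows. Reported swelling severity may rise slightly, and a functional grade is less objective than a ruler measurement. The second costs a label and a footnote, and leaves functional severity of swelling unreported. The same edit can align the Grade 4 wording for swelling and correct the SAP 5.9 pointer to Appendix I, since the SAP's scale is in Appendix II.

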8.7.2.2 Unsolicited Adverse Events

All the unsolicited AEs occurring during the proscribed collection period in the study, will be recorded, regardless of their assessment of relatedness by the investigator.

The original verbatim terms used by investigators to identify AEs in the eCRFs will be mapped to PT using the MedDRA dictionary. The unsolicited AEs will then be grouped by MedDRA PT into frequency tables according to SOC. All reported AEs, as well as AEs judged by the investigator as at least possibly related to IP, will be summarized by treatment group, according to SOC and PT. When an unsolicited AE occurs more than once for a participant, the maximum severity and strongest relationship to the treatment group will be counted.

Only treatment-emergent AEs will be summarized (i.e., excluding those after a participant has given informed consent, but before vaccination).

Unsolicited AEs will be summarized by alphabetic SOC and preferred term as follows:

- Any unsolicited AE
- Related ("possibly" or "probably" related) unsolicited AEs
- Serious adverse events
- Related ("possibly" or "probably" related) SAEs
- Adverse events of special interest
- Medically-attended AEs
- Related MAAEs
- Unsolicited AEs leading to withdrawal
- Any AE leading to death

Listings of all AEs will be provided by participant.

Combined solicited and unsolicited AEs: Solicited AEs continuing beyond 7 days after vaccination will be coded by MedDRA and combined with the unsolicited AEs. A summary of participants with all combined solicited and unsolicited AEs, by SOC and PT, will also be provided.

8.7.3 Clinical Laboratory Data

No clinical safety laboratory data will be collected in this study.

8.7.4 Physical Examinations

Physical examinations by body system include a complete examination at screening and directed examinations at Days 1, 8, 15, 22, and 183. Physical examination data will be listed.

8.7.5 Vital Signs

Vital signs including temperature, blood pressure, respiratory rate, and heart rate at screening and pre- and postvaccination on Day 1 will be summarized by treatment group.

8.7.6 Prior and Concomitant Medications

Prior and concomitant medications will be coded to preferred drug name using the World Health Organization DRUG dictionary and summarized by treatment group for the safety population.

8.7.7 Other Safety Variables

None.

8.7.8 Subgroup Analysis

Except for lot consistency analyses, PXVX0317 lots will be pooled as the PXVX0317 treatment group. Summaries will pool all age groups and will be repeated separately for each age group. Analyses of the primary immunogenicity and safety endpoints will also be summarized by sex, race, and ethnicity along with treatment group.

8.7.9 Interim Analysis

No formal interim analysis is planned. The SMC (Section 7.6) will review aggregated, blinded safety data after the 300th enrolled participant passes Day 29, and again after the last enrolled participant passes Day 29.

9 DATA HANDLING AND RECORD KEEPING

9.1 Source Documents and Access

Source data are all information, original records of clinical findings, and observations in a clinical study necessary for the reconstruction and evaluation of the study. The source documentation requirements described below apply to all source documentation and study

PXVX0317 Vaccine EBSI-CV-317-004, Version 5.0 20 Mar 2023

records in any form, including those maintained in the institution's electronic health record system, if applicable.

The investigator/institution will maintain adequate and accurate source documents and study records that include all pertinent information related to participants' participation in the study, including details but not limited to signed and dated notes on consenting, eligibility, medical history, study assessments, IP administration, AEs, concomitant medications, participant follow-up information and other relevant observations.

Source data should be attributable, legible, contemporaneous, original, accurate, and complete. Changes to source data should be traceable, should not obscure the original entry and should be explained if necessary (eg, via an audit trail).

The investigator/institution shall permit study-related monitoring, audits, IRB review, and regulatory inspection(s), providing direct access to source data/documents.

Records from the study that identify the participant will be confidential except that they may be given to and inspected by sponsor (or designee), the IRB, the FDA, EMA, and other government agencies as appropriate and will not otherwise be released except as required by law. All information provided to the investigator by the sponsor is to be considered confidential unless otherwise stated.

9.2 Data Management

A validated, EDC system will be used during the study. Data management activities to be performed for the study will be described in detail in the Data Management Plan (DMP) documents.

9.3 Data Collection and Discrepancy Management

Data collected during the study will be recorded in the eCRFs designed for this study. Investigational sites will have the responsibility for capturing and maintaining accurate eCRF data, records, and relevant source documentation, as well as conforming to procedures established by the sponsor around system access/security and ensuring a data audit/edit trail for data corrections. All source documents will be verified by the study monitor for accuracy. Information from external sources such as laboratory data, images, etc. as defined in this protocol will be collected and maintained outside the EDC and reconciled with the eCRF data periodically (as applicable). As data are entered into the eCRF, automated edit checks will validate data. Additionally, manual reviews will be performed for data discrepancy by the monitor and queries will be generated into the EDC system. After clinical sites respond to queries and data corrections are made and reviewed by the monitor, the investigator will review and electronically sign the eCRF for each participant. The sponsor will review data for accuracy, completeness, and consistency during the conduct of the study and prior to database lock. For further information on eCRFs, refer to the CRF Completion Guidelines. Details on data handling will be described in the DMP.

